**19. Do you experience NOT injury related pain before/during/after mountain biking?**

before     during     after     no

**20. If you experience NOT injury related pain, where is it located?**

knee     neck     lower back     hip     buttocks

other \_\_\_\_\_

**21. Treatment of muscle soreness/problems**

massage lotions     electrostimulation     supplements     NSAID pain relievers  
 cooling applications     other \_\_\_\_\_  
*(i.e. Ibuprofen, dafalgan, aspirin, voltaren)*

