## **2. Methods**

A survey (as outlined below) of mountain biking related injuries will be conducted on the participants of the Swiss Epic mountain bike event in 2017 held in Valais. The retrospective questionnaire is designed in accordance with existing literature ((Gaulrapp et al., 2001; Lareau and McGinnis, 2011), will include 25 questions and will be translated into English, French, Italian, Spanish and German. The participants will be asked to tick the most appropriate answer. The questionnaire aims to assess the athletes' 1) basic demographics, riding level and years of experience, 2) number of races per year and mean hours of training per week, 3) number and kind of suffered injuries related to mountain biking and medical treatment requirement, 4) and amount and kind of protective gear items.

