## **3. Statistical analysis plan**

Data analyses will be performed using the Statistical Package for Social Sciences (SPSS), version 24.0 (IBM Corporation, Armonk, NY, USA).

Descriptive statistics [means  $\pm$  standard deviations (SD) and relative frequencies (%)] will be retrieved. Pearson correlations will be used to assess correlations between the outcome variables. Chi-squared tests will be applied to determine group differences of injury prevalence and the occurrence of severe, respectively mild injury events. Multivariate logistic regressions will be performed to evaluate predictive factors among the outcome variables (independent variables) of severe injury events (dependent variable; no severe injury = 0 versus severe injury = 1) in elites and amateurs separately. Independent samples t-tests will be used to evaluate mean group differences in demographics, and training and injury related variables between the elite and the amateur mountain bikers. P-values  $< 0.05$  will be considered as statistically significant. According to Cohen (1992), effect sizes will be calculated for the correlation analyses and defined as follows;  $r = 0.20$  small,  $r = 0.50$  medium,  $r = 0.80$  strong.

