## Mountain biking Injury Questionnaire

*Thank you for agreeing to take part in this important questionnaire about mountain biking injuries. The information we can obtain from this survey may help to improve the knowledge about injury prevalence in mountain biking. With this knowledge, it may be possible to improve safety in future and prevent injury.*

*Be assured that all answers you provide will be kept in the strictest confidentiality. This survey is anonymous. Do not write your name on the survey.*

*Please tick only the most correct answer.*

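### Item 21 cannot give a reliable percentage for NSAID use or any other soreness treatment, and the direction of the error is unknown

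*Combined protocol and SAP*

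**What the plan says.** Item 21, headed "Treatment of muscle soreness/problems", offers six answers: massage lotions, electrostimulation, supplements, "NSAID pain relievers", "cooling applications" and a free-text 'other'. It prints a line of examples, "i.e. Ibuprofen, dafalgan, aspirin, voltaren". It has no box for no treatment, no skip condition and no space to name the drug taken.

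The questionnaire's introduction tells riders "Please tick only the most correct answer", and section 2 (Methods) says the same: "The participants will be asked to tick the most appropriate answer". Neither makes an exception for item 21.

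Item 19 ("Do you experience NOT injury related pain before/during/after mountain biking") offers a 'no', as do items 18, 22, 23 and 24.

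Section 3 (Statistical analysis plan) promises "relative frequencies" in general terms. It sets no denominator and no rule for blank answers, and it names no analysis of item 21. The four assessment aims in section 2 do not mention soreness treatment or analgesic use.

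**The concern.** Three features of the item act on the same percentage.

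- **Mixed drug class.** A rider who takes only paracetamol and follows the printed examples ticks the NSAID box. The drug is not recorded and no other item asks about analgesics, so the two groups cannot be separated later.
- **No 'none' answer.** A rider who treats nothing has no printed answer. A blank may mean no treatment or a skipped question.
- **One tick.** A rider who uses an NSAID together with, say, a massage lotion must choose between them, and some NSAID users will be recorded elsewhere.

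The survey is anonymous, so riders cannot be asked afterwards what they meant. At stake is whether a published percentage for NSAID use, or for any other treatment in this item, would mean what its label says.

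**Working it through.** The documents give no sample size, no rate of NSAID use and no non-response rate, so there is no stated figure to reproduce. The check below asks only which way the error runs. **Every input value is an assumption.**

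Inputs:
- u = true share using NSAIDs, set at 30%.
- w = share using paracetamol only who tick the NSAID box, 0 to 10%.
- s = share of NSAID users whose single tick goes to another option, 0 or 25 to 50%.
- n = share using no treatment, who leave the item blank, 20 to 40%.
- b = 1 if those blanks are dropped from the denominator, 0 if they are kept. The plan does not say which.

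Formula: reported share = [u(1 − s) + w] / (1 − n·b).

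| Case | Lowest | Highest | Bias (points) |
|---|---|---|---|
| Drug mix only (w = 5–10%, s = 0, blanks kept) | 0.30 + 0.05 = 35% | 0.30 + 0.10 = 40% | +5 to +10 |
| Blanks dropped only (w = 0, s = 0) | 0.30/0.80 = 37.5% | 0.30/0.60 = 50% | +7.5 to +20 |
| Drug mix (w = 5–10%) and blanks dropped, s = 0 | 0.35/0.80 = 44% | 0.40/0.60 = 67% | +14 to +37 |
| Single tick (s = 25–50%), w = 0–10%, blanks kept | 0.30 × 0.50 = 15% | 0.30 × 0.75 + 0.10 = 32.5% | −15 to +2.5 |
| Single tick (s = 25–50%), w = 0–10%, blanks dropped | 0.15/0.80 = 19% | 0.325/0.60 = 54% | −11 to +24 |

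The first three rows leave the single-tick rule out and are all positive. Once the rule is included, as the form requires, the range spans zero whether blanks are kept or dropped.

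The denominator effect is not specific to NSAIDs. Dropping blanks multiplies the percentage for every option by 1/(1 − n), which is 1.25 at n = 20% and 1.67 at n = 40%.

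**The case against.** The strongest defence is that nothing planned depends on this item. The study is about the causes and effects of injuries, none of the four aims covers soreness treatment, and the planned tests and regressions on injury and severity do not need it. This stands, and it limits the point to the descriptive frequencies for item 21. Those frequencies still fall within the general promise in section 3.

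Some ambiguity over blanks can be reduced. A rider can write 'none' under 'other', and one who answers the neighbouring items but leaves item 21 empty can be told apart from one who abandoned the form. This also stands, although an isolated skip remains ambiguous.

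The example line is printed after 'other' in the extracted text, so attaching it to the NSAID box is an inference. It is the natural one. If the examples did belong to 'other', the form would be sending ibuprofen and aspirin users away from the NSAID box, which is no better.

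A reader might infer that the survey will overstate NSAID use. For example, assume true use of 20%, paracetamol-only use of 5 to 15% and untreated riders of 20 to 50%. The box would then show 25/80 = 31% to 35/50 = 70%. That range needs blanks to be dropped, which the plan does not specify; with blanks kept, the same inputs give 25 to 35%. It also assumes that every NSAID user ticks the NSAID box, which the single-tick instruction makes unlikely. The documents do not support a fixed direction.

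A reader might also infer that nothing can be done at analysis. That goes too far: the category can be relabelled, and results can be shown with blanks counted as no treatment and then as missing. Only the split by drug class is lost for good.

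**Conclusion.** The point holds as a limited one. As written, item 21 cannot give a reliable percentage for NSAID use, and the missing 'none' and the single tick weaken the percentages for its other options too. The sign of the error is not determined by the documents. With assumed true use of 30%, the bias under the single-tick rule runs from −15 to +24 points; these figures illustrate direction and do not predict size.

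The drug-class part rests on dafalgan being paracetamol and on the examples belonging to the NSAID box. The missing 'none' and the single-tick conflict rest on the documents alone and stand without those assumptions. The injury and severity comparisons are untouched. Priority is low.

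**What to change.** Before fielding, in item 21:

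- add a 'none' box;
- instruct riders to tick all that apply for this item;
- either relabel the analgesic box as pain relievers, keeping the four drugs as examples, or give paracetamol its own box;
- print the examples next to the option they illustrate.

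The multiple-tick instruction is essential if boxes are added, because more boxes under a single-tick rule would split the answers further. Section 3 should also state the denominator for this item.

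If the form can no longer be changed, report the category as any pain reliever, use all respondents as the denominator, and show blanks as a separate category. This does not undo the single tick, so the text should say that the percentage is the share of riders who chose that option as their one answer.

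The cost is a slightly longer item in each of the five language versions, and the change is cheapest before translation.

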**22. Do you use warming up cremes/ointments before the race?**

yes     no

**23. Do you use any cremes/ointments after the race?**

yes     no

**24. Do you use any Perskindol products?**

yes     no

**25. If yes, before/during/after race?**

before     during     after
